4.7. Safety Analyses

Safety analyses will be conducted on the TTS. All safety analyses will be performed on the subgroups of relapsing Ig-pretreated patients and Ig-naïve patients as well as overall.

4.7.1. Extent of exposure

4.7.1.1. Patient level analyses

The extent of exposure to IMPs will be summarized on the patient level using the following variables:

- Duration of study participation (month) from signing of informed consent to EOS (see section [5.7.3](#))
- Duration of treatment exposure (month) from the first day of IMP administration to EOS (see section [5.7.3](#))
- Total number of courses
- Total number of infusions (see section [5.7.3](#))

- Cumulative dose over all infusions (g and g/kg) (see section [5.7.3](#))
- Average dose per course (g and g/kg) (see section [5.7.3](#))
- Maximum dose over all infusions (g and g/kg)
- Maximum flow rate over all infusions (mL/kg/h)

4.7.1. 2. Course level analyses

The extent of exposure to IMPs will be summarized on the course level using the following variables:

- Total number of infusions (At course 1, all subsequent courses and all courses taken together)
- Course dose in g and g/kg (At course 1, all subsequent courses and all courses taken together)
- Initial flow rate of the first course infusion (mL/kg/h)
- Duration of initial flow rate of the first course infusion (min)
- Maximum flow rate over all infusions (mL/kg/h)
- Duration of the course in days (At course 1, all subsequent courses and all courses taken together)

4.7.1. 3. Infusion level analyses

The extent of exposure to IMPs will be summarized on the infusion level using the following variables:

- Dose (g and g/kg)
- Initial flow rate (mL/kg/h)
- Maximum flow rate (mL/kg/h)
- Duration of the infusion (min)

For patients who experienced at least one infusion with an interruption/discontinuation or a decreased flow-rate, a listing will be provided presenting information on all infusions received during the given course.

In all three analysis levels, dose (g and g/kg) will be derived based on the prescribed administered volume reported in the CRF:

- Dose (g) = Daily volume administered (mL) x batch concentration (i.e. 0.1 g/L)
- Dose (g/kg) = Dose (g) / body weight (kg) at the start of the course

A listing will be provided with the presented variables of each analysis level (patient, course, infusion).

4.7.2. Adverse events

All AEs occurring during the study will be classified by PT and SOC using the version 17.1 of the MedDRA.

Seriousness	Serious if one of the follow-ups is serious / Non-serious otherwise
Seriousness criterion	For each of the criteria listed below: Yes if at least one of the follow-ups had Yes for the corresponding criterion / No otherwise 
▪ Results in death▪ Life-threatening▪ In hospitalisation or prolongation of existing hospitalisation▪ Persistent or significant disability / incapacity▪ Congenital anomaly / birth defect▪ Important medical event
Start date time	Start date time of the first follow-up
End date time	End date time of the last follow-up
Ongoing	Yes if last sequence follow-up is ongoing / No otherwise
Did the AE start within 72h after an infusion?	Yes if the first follow-up started within the first 72h after an infusion / No otherwise
Intensity	Maximum (Intensity of follow-ups) Increasing order of importance: Mild / Moderate / Severe
Action taken	Maximum (Action taken of follow-ups) Increasing order of importance: None / Dose changed / Interruption of IMP / Discontinuation of IMP
Corrective medication	Yes if at least one of the follow-ups had a corrective medication / No otherwise
Relationship to study drug	Yes if at least one of the follow-ups had a relationship to study drug assessed as Yes / No otherwise
Outcome	Maximum (Outcome of corresponding follow-ups) Increasing order of importance: Unknown / Recovered without sequela / Recovered with sequelae / Recovering / Not recovered / Fatal

AEs will be classified as Pre-treatment or Treatment-Emergent according to the date of onset:

- Pre-treatment AE defined as an event with a date-time of onset before the first infusion date-time.
- TEAE defined as any event with a date-time of onset on/after the start date-time of the first infusion.

Treatment emergent adverse event flag

The following rules for the derivation of the TEAE status will be used in the order of display:

- If the date-time of the AE onset is known: TEAE = “Yes” if AE onset date-time \geq start date-time of first IMP infusion / “No” otherwise
- If the date-time of the AE onset is not known but the complete date of the AE onset is known:

- TEAE = “Yes” if AE onset date > start date of first IMP infusion
- TEAE = “Yes” if AE onset date = start date of first IMP infusion and investigator’s assessment of the time of onset ≠ “Before infusion”
- TEAE = “No” otherwise
- If the date of AE onset is a partial date and the investigator’s assessment of the time of onset is not missing: TEAE = “Yes” if investigator’s assessment of the time of onset “During infusion”, “≤72h” or “>72h”
- If the date of AE onset is a partial date and the investigator’s assessment of the time of onset is missing:
 - TEAE = “Yes” if last possible date in the period defined by the partial date ≥ start date of first IMP infusion / “No” if the last possible date in the period defined by the partial date < start date of first IMP infusion
- TEAE = “Yes” otherwise

Temporally associated adverse events (TAAEs)

TAAE will be defined according to the item “Schedule” collected in the eCRF. They will include all adverse events with Schedule “During infusion”, “Within 72 hours after the end of the infusion”. If Schedule is missing then the event will be classified as TEAE by default.

Other significant AEs

Other Significant AEs are based on the definition of relevant AESIs (Adverse Events of Special Interest) for I10E. They are defined as standardized MedDRA queries (SMQs) of interest on the narrow scope, these are:

- Anaphylactic reaction (SMQ) [20000021] narrow scope
- Anaphylactic/anaphylactoid shock conditions (SMQ) [20000071] narrow scope
- Noninfectious meningitis (SMQ) [20000134] narrow scope
- Embolic and thrombotic events, vessel type unspecified and mixed arterial and venous (SMQ) [20000083] narrow scope
- Acute renal failure (SMQ) [20000003] narrow scope
- Hemolytic disorders (SMQ) [20000019] narrow scope
- Eosinophilic pneumonia (SMQ) [20000157] narrow scope
- Interstitial lung disease (SMQ) [20000042] narrow scope

Pre-treatment Adverse Events

Pre-treatment AEs will be listed for all enrolled patients.

Summary of treatment Emergent Adverse Events (TEAE)

A summary of the total number of TEAEs, and number and percentage of patients with at least one TEAE will be presented. This summary will include the number and percentage of patients having at least one TEAE as well as the absolute number of TEAEs in each AE category:

- TEAEs
- Serious TEAEs by seriousness criterion

- Drug-related TEAEs
- TAAEs
- TEAEs by severity (Mild / Moderate / Severe)
- TEAEs by Action taken with IMP (None / Dose reduced / Dose increased / Discontinuation of IMP / Temporary interruption of IMP, (the action could also be a decrease of infusion flow rate))
- TEAEs by outcome (Resolved without sequelae / Resolved with sequelae / Not recovered / Recovering / Fatal / Unknown)
- Other significant AEs

A similar summary table will be produced for TAAEs as well as drug-related TEAEs and Serious TEAEs.

All TEAEs, SAEs, TAAEs and drug-related AEs will be summarized by SOC and PT, showing number of TEAEs, and number and percentage of patients with at least one TEAE, sorted by decreasing incidence of SOC and PT within SOC in the column “overall”.

Summary of TEAEs will also be presented by relevant subgroups (e.g., by age group [<65 years and ≥ 65 years], sex, race [white, non-white and unknown], and BMI [<30 kg/m² and ≥ 30 kg/m²]).

The rate of TEAEs by patient, course, infusion and drug-related AEs by course will be presented and sorted by decreasing incidence of PT in the column “overall”. Rate is defined as the number of events for unique PTs divided by the total number of patients, courses and infusions respectively.

Duration of most-common (those which occurred in at least 10% of the patients in the overall safety population) drug-related AEs will be calculated as is outlined in Section [5.7.2](#) and will be presented with descriptive statistics on recovered AEs (i.e., AEs with an outcome of “Recovered without sequelae” or “Recovered with sequelae”). Statistical unit of analysis will be the individual who recovered from drug-related AE. No imputation will be performed for the purposes of computing duration.

The time between the stop time of the last administration of IMP (before the onset of event) to the onset of the drug-related AEs will be calculated (in days) as is outlined in Section [5.7.2](#) and will be presented with descriptive statistics using the individual drug-related AE as statistical unit.

All Serious TEAEs, drug-related AEs, AEs leading to dose changes (action taken is not missing, “None” or “Not-applicable”) or discontinuation of IMP, and other significant TEAEs will be listed. These listings will include the event duration as well as the time elapsed (in days as is outlined in Section [5.7.2](#)) between the stop time of the last administration to the onset of the event.

The rate of of drug-related TEAE will be presented by course number and overall. This rate will be calculated as the ratio between the number of TEAEs starting during a course and the overall number of patients treated at the corresponding course.

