9.5.3. Adverse Event recording and reporting

Period of (Serious) Adverse Event Data Collection:

In order to ensure complete safety data collection, recording and reporting, all (S)AEs occurring during the study, i.e. after signature of the Informed Consent, must be recorded, even if no study drug was administered. These include all AEs occurring, recurring, or worsening after the signature of the informed consent. The period of observation for the study is from the screening visit to the end of study visit.

If the Investigator becomes aware, after that period, of any unusual safety information or any safety information that appears to be drug related involving a patient who had participated in the study, even after the patient completes the study, he/she should contact the sponsor to determine how it should be documented and reported.

Recording and Description of (Serious) Adverse Event:

All AEs occurring after signature of the informed consent until the end of study visit will be recorded in the appropriate pages of eCRF, including AEs occurring during the screening period and before the first administration of study drug, other than baseline findings which will be recorded as medical history.

Each individual AE is to be listed as a separate entry on the eCRF AE form. The Investigator will provide information on dates of onset and resolution, seriousness, severity, frequency, action(s) taken with regard to corrective therapy or to the study drug, outcome and relationship to the study drug. The Investigator must report to the Sponsor or its designee all AEs that occur during the study from the time the written informed consent is given until the EOS visit or premature termination, regardless of their relationship to the study drug. Apart from AEs clinically observed by the Investigator, the patient will be given the opportunity to report AEs spontaneously. A general prompt will also be given to detect AEs, e.g. "Did you experience any illness or unusual symptom since your last visit?"

Follow-up of Adverse Events:

All AEs and SAEs assessed as not related to study medication, including clinically significant laboratory tests or physical examination findings, must be followed until the event resolves, the condition stabilizes, the event is otherwise explained, or the final study visit occurs, whichever comes first.

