3. GENERAL STATISTICAL CONSIDERATIONS

3.1. Description of Variables

Continuous data will be described using number of valid observations, number of missing observations, mean, standard deviation, median, quartiles, minimum and maximum.

Categorical data will be described using number of missing observations, number of valid observations per category and percentage. Number of missing observations will not be taken into account for the calculation of percentages.

For descriptive statistics, the following number of decimal places (dps) will generally be applied:

- 3 dps for values in [0, 0.9995)
- 2 dps for values in [0.9995, 9.995)
- 1 dp for values in [9.995, 99.95)
- 0 dp for values ≥ 99.95

For negative values the same rule will be followed using the absolute value.

For original case report form (CRF) variables the minimum and maximum will use the same number of dps as the raw data. Statistics on count variables (e.g. number of infusions) will generally be presented with 1 dp while the minimum and maximum will be presented without dp. Percentages will be presented with 1 dp. Exceptions from these rules might be applied when necessary.

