3.2. Handling of Missing Data and Outliers

Regarding the primary criterion, a patient will be also considered as a non-responder if the patient is withdrawn due to lack of efficacy of the treatment (insufficient response to the investigational medicinal product [IMP]). In all other cases, if the INCAT score at EOS visit is missing, then the Last Observation Carried Forward (LOCF) approach will be applied and the last available adjusted INCAT disability score will replace the missing value at EOS visit.

The LOCF approach will also be used to handle the missing data of the secondary endpoint for adjusted INCAT and response at week 12 only.

When AEs are documented in the diary, dates of AE onset may be missing and as a result, TAAE cannot be defined. For AEs with a missing or incomplete start date, the response to the question “Did the AE start within 72 hours of an infusion” will be used for determining if the AE is temporally related to the infusion.

Partial dates of first symptoms and partial dates of diagnosis will be imputed by 15 if only the day is unknown and by 1st July if day and month are unknown. No imputation will be done if the year is unknown.

For the calculation of duration of AEs, partial start and end dates will be imputed with the first and last possible date within the period defined by the partial date, respectively. In general, no

calculation of duration will be made if either the start date or stop date is missing, i.e., cannot be imputed using pre-determined rules. No other general rules for the replacement of missing data are planned.

Data listings will always show the original CRF reported values and not the imputed values.

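### An adverse event with no causality recorded on any follow-up is derived as not related, so drug-related counts, percentages and rates can only be equal or lower

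*SAP*

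**What the plan says.** The derivation table in SAP 4.7.2 sets the relationship flag to *Yes* "if at least one of the follow-ups had a relationship to study drug assessed as" *Yes*, and to *No* otherwise. The flag has two levels and none for missing or unknown.

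No other rule covers a blank. SAP 3.2 deals with missing INCAT scores, partial dates and temporal association, then states: "No other general rules for the replacement of missing data are planned". SAP 3.1 promises a missing count for categorical variables ("Categorical data will be described using number of missing observations, number of valid observations per category and percentage"), but the derived flag has no missing value left to count.

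The flag defines these outputs in SAP 4.7.2:
- the drug-related line of the TEAE summary and a separate drug-related summary;
- the SOC/PT table ("All TEAEs, SAEs, TAAEs and drug-related AEs will be summarized by SOC and PT");
- the rates by course;
- the duration summary for common drug-related events and the time-to-onset summary;
- the drug-related listing.

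On collection, Protocol 9.5.3 has the investigator supply, for each event, items that include "outcome and relationship to the study drug".

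**The concern.** A blank is the absence of a judgement. The rule turns it into a negative judgement that no investigator made. Because only *Yes* places an event in the drug-related outputs, the misclassification runs in one direction for counts, percentages and rates. The trial has a single arm, so there is no comparator in which the same loss would occur. After derivation, the drug-related tables cannot show how many events were classed as not related by default.

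Other parts of the same section treat missing information differently. The treatment-emergence rules end by assigning *Yes* to unresolved cases, and the outcome row keeps an Unknown level. Causality has neither.

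**Working it through.** The documents state no figure that depends on this rule, so there is none to reproduce. The check applies the rule to each possible set of records and then sizes the effect.

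**Inputs.** The rule is from SAP 4.7.2. The planned number treated is 42 (Protocol 12.3). The share of events with blank causality, the number of TEAEs and the proportion related are not in the documents.

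**Step 1: the rule applied.**

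| Causality across follow-ups | SAP rule | Blank on all records counted as related |
|---|---|---|
| Yes | Yes | Yes |
| No | No | No |
| blank, Yes | Yes | Yes |
| blank, No | No | No |
| blank | No | Yes |
| blank, blank | No | Yes |

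Only events with no assessment on any record differ. A partly blank event is classified by what was recorded.

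**Step 2: direction.** Every event flagged by the SAP rule is also flagged by the alternative, and the denominators (patients, courses, infusions) do not depend on causality. Counts, percentages and rates under the SAP rule are therefore equal or lower. This does not carry over to summary values of duration or time to onset: losing an event can move a mean or median either way.

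**Step 3: patient level.** One patient is 1/42 = 2.4 percentage points, two are 2/42 = 4.8, and three are 3/42 = 7.1. A patient counts here only if he or she has no other related event in the same row.

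**Step 4: the cut for the duration table.** That table keeps common drug-related events, "those which occurred in at least 10% of the patients in the overall safety population". With 42 patients, 10% is 4.2, so 5 patients are needed. If the cut is applied to drug-related occurrences, losing one patient takes a preferred term from 5/42 = 11.9% to 4/42 = 9.5%, and it leaves the table.

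**Step 5: event level, illustration only.** Assume 100 TEAEs, with 30% of assessed events related.

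- SAP rule: (100 − blanks) × 0.30
- All-blank counted as related: the same figure + blanks
- Blanks related at the same 30%: 100 × 0.30 = 30.0

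| Blank (assumed) | SAP rule | All-blank as related | Blanks related at 30% |
|---|---|---|---|
| 1% | 29.7 | 30.7 | 30.0 |
| 5% | 28.5 | 33.5 | 30.0 |
| 10% | 27.0 | 37.0 | 30.0 |

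On these assumptions the SAP rule falls short by 0.3, 1.5 and 3.0 events. The alternative overshoots by 0.7, 3.5 and 7.0. With no blanks, all three agree.

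**The case against.** The strongest reply is that the case should hardly arise. The investigator must give causality for each event. For SAEs it is part of the minimum notification content (Protocol 9.5.4.1). Computerised checks raise queries, SAE reports are reconciled with the pharmacovigilance database, a data review meeting precedes lock (Protocol 11.2), and the monitor checks completeness (Protocol 16.2). This stands as a limit on size. It does not correct the rule that applies to any blank left after those steps, and Protocol 11.1.2.4 foresees that some missing data will remain.

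A second reply is that the table is written to combine follow-ups, not to handle missing data. Across recorded values it is cautious, since one *Yes* outweighs any number of *No*. The seriousness and corrective-medication rows use the same form. That is right, and nothing suggests that the wording was chosen to favour the product. The effect on an all-blank event is the same.

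The contrast with other rules also needs care. The SAP has no uniform cautious default: "If Schedule is missing then the event will be classified as TEAE by default", which keeps the event in the TEAE tables but does not count it as a TAAE. The case against the causality rule does not depend on that contrast.

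A reader might infer more than the documents support:
- *That the safety objective rests on these tables.* The listed safety endpoints (Protocol 3.2.3, SAP 2.5.3) are TEAEs, SAEs, TAAEs and changes in vital signs and laboratory values. None is defined by causality, and an event with blank causality still counts in those analyses.
- *That the event disappears unseen.* SAP 3.2 and 5.1 have listings show all data as originally reported, so the blank can be found there. The event is absent only from the drug-related outputs.
- *That every drug-related table is lowered.* Duration and time-to-onset values can move either way.

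**Conclusion.** The point holds as a minor one. An event with causality blank on every record is reported as not related, and nothing in either document overrides that. Drug-related counts, percentages and rates are equal or lower as a result, and the event is missing from the drug-related listing.

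The size cannot be derived from the documents. It may be zero, and the collection and query steps make it likely to be small. The figure of 2.4 points per patient assumes 42 treated patients and applies only where the patient has no other related event in the row. The event-level illustration rests on assumed numbers throughout. The primary efficacy analysis and the TEAE, SAE and TAAE endpoints do not change.

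**What to change.** Reword the relationship row in SAP 4.7.2. Derive *Yes* if any follow-up is *Yes* or if causality is missing on all of them. Derive *No* only if at least one follow-up records *No* and none records *Yes*. Report the number of events classed as related because causality was missing, so that the event count based on recorded assessments can be recovered by subtraction. A separate missing row would also remove the false negative, but it leaves the drug-related count itself as it is now.

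The cost is one line of SAP wording, the matching change in the derivation program, and one extra reported number. The downside is a possibly slightly higher drug-related count, since some blank events may not be related. If no causality is missing at lock, no result changes.

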5.7.2. Safety

Adverse Event Duration

The duration of AEs will be calculated as:

$$\text{AE Duration (days)} = \text{AE stop date} - \text{AE start date} + 1$$

Similar formula will be used for any duration-related calculations.

Time to AE onset

The time to onset of an AE since the previous infusion will be calculated as:

$$\text{Time to AE onset (days)} = \text{AE start date} - \text{Date of previous IMP infusion} + 1$$

Similar formula will be used for any time to event-related calculations.

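### The SAP's worst-record rule for adverse event outcome tabulates a multi-record event that has recovered as unresolved, while its end date and ongoing flag come from the last record.

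*SAP*

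**What the plan says.** The table in SAP section 4.7.2 states how the follow-up records of one adverse event are reduced to a single analysis record. Three rows matter here.

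- **Outcome** is "Maximum (Outcome of corresponding follow-ups"), taken over this increasing order: "Unknown / Recovered without sequela / Recovered with sequelae / Recovering / Not recovered / Fatal".
- **End date** is "End date time of the last follow-up".
- **Ongoing** is Yes "if last sequence follow-up is ongoing" and No otherwise.

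The combined outcome is then used in two places in the same section. First, treatment-emergent events are tabulated by outcome, and "A similar summary table will be produced for TAAEs as well as drug-related TEAEs and Serious TEAEs". Second, the duration of the most common drug-related events "will be presented with descriptive statistics on recovered AEs", meaning events whose outcome is one of the two recovered categories.

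Duration itself does not depend on outcome: SAP section 5.7.2 computes it from start and stop dates. For the listings of serious, drug-related and certain other events, section 4.7.2 adds: "These listings will include the event duration as well as the time elapsed".

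Nothing else in the SAP, including the list of changes in section 4.10, lets a later recovery replace an earlier unresolved status.

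**The concern.** A maximum suits attributes where the worst value reached is what one wants to report, such as intensity, seriousness or action taken. Outcome is different, because it is read as the final status of the event. Under a maximum, once any record says Recovering or Not recovered, no later record of recovery can change the tabulated result.

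Improvement over time is an ordinary course for an adverse event. Protocol section 9.5.3 has events followed, in many cases until they resolve, and asks for a resolution date where a related event has resolved. The rule goes wrong in exactly that situation.

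Three outputs are exposed:

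- The by-outcome rows for treatment-emergent events, and the similar tables for temporally associated, drug-related and serious events, can count resolved events as unresolved.
- The duration summary of common drug-related events can lose recoveries that it was meant to describe.
- A listing can show a completed duration for an event that the table counts as unresolved.

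**Working it through.** There is no stated figure to reproduce. The check applies the SAP's rule literally and counts the patterns in which it gives the wrong status.

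**Inputs (SAP section 4.7.2).** Ranks in the stated order:

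| Outcome | Rank |
|---|---|
| Unknown | 0 |
| Recovered without sequelae | 1 |
| Recovered with sequelae | 2 |
| Recovering | 3 |
| Not recovered | 4 |
| Fatal | 5 |

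**One event.** Record 1: Not recovered, ongoing. Record 2: Recovered without sequelae, end date given, not ongoing.

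- Outcome = max(4, 1) = 4, so Not recovered.
- End date = the date on record 2.
- Ongoing = No, from record 2.

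The combined record has an end date and is not ongoing, yet its outcome is Not recovered. It fails the recovered-only condition for the duration summary, although stop date − start date + 1 can be calculated.

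**Two-record patterns ending in recovery.** The first record is any non-fatal status {0, 1, 2, 3, 4} and the last is {1, 2}: 5 × 2 = 10 patterns. The maximum is 3 or 4 whenever the first record is 3 or 4: 2 × 2 = 4 patterns. So 4 of 10 are tabulated as unresolved (3→1, 3→2, 4→1, 4→2).

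**Only patterns with no earlier recovered record.**

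- Two records: the first is {0, 3, 4}, giving 3 × 2 = 6 patterns. The same 4 are wrong.
- Three records: 3 × 3 × 2 = 18 patterns. The result is right only if both earlier records are Unknown (1 × 2 = 2), so 16 are wrong.

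**Alternative rule.** Take Fatal if any record is fatal, otherwise the last known outcome, otherwise Unknown.

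- Patterns ending in recovery that are reported as unresolved: 0 of 10.
- All two-record patterns with a non-fatal first record: 5 × 6 = 30. The current and alternative rules differ in 6. Four are the errors above. The other two are 2→1 (with sequelae becomes without) and 4→3 (Not recovered becomes Recovering), and neither crosses between resolved and unresolved.
- Relapse: a recovered record followed by Recovering or Not recovered is unresolved under both rules.

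**A final Unknown after a known non-fatal status.** There are four such patterns: 1→0, 2→0, 3→0 and 4→0. The current rule keeps the known status in 4 of 4, and so does the alternative. A plain last-record rule would turn all 4 into Unknown.

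These counts describe how the rule behaves. They are not expected frequencies.

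**The case against.** **It may never act.** Protocol section 9.5.3 makes each adverse event a separate eCRF entry, and section 11.1.2.5 speaks of modifying existing events. If an event is held as one updated entry, there is nothing to take a maximum over. This stands as a limit on the effect. It does not remove the point, because the SAP table provides for several follow-ups and for a last one in sequence.

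**The pattern fractions do not measure the problem.** This also stands. The share moves from 4 of 10 to 4 of 6 to 16 of 18 depending on which patterns are counted. The number of affected events cannot be obtained from the documents.

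**Worst case is a conservative convention.** The same table uses it for seriousness, intensity, action taken, corrective medication and relationship. For outcome it can only overstate unresolved events. That limits the harm, but it does not reconcile the outcome with an end date and ongoing flag drawn from another record.

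**The duration effect is narrow.** The event must be drug-related, of a type seen in at least 10% of patients, held in several records, and unresolved before it recovered. The SAP also makes the unit of that summary the individual who recovered, not the event. Both qualifications are fair.

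**Listings allow a check.** SAP section 3.2 says listings show reported and not imputed values, but it does so in the context of missing data, and the SAP does not say which outcome value the adverse event listings display. A reader may be able to trace a single event; the tables would still be wrong.

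**The fix overrides a deliberate Unknown.** Protocol section 9.5.3 requires the investigator to document the outcome as unknown when follow-up cannot be obtained. Keeping the last known status hides that entry and leaves outcome and ongoing flag on different records in that case. The current rule already does the same in 4 of 4 patterns, so the fix adds no new conflict. Whether a final Unknown should show in the tables is a separate choice for the sponsor.

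**Conclusion.** The point holds. As written, the outcome rule gives the wrong final status to any adverse event that has several records, at least one of them Recovering or Not recovered, and ends in recovery. The rest of the same table can describe that event as ended and not ongoing.

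The conclusion rests on reading the SAP's ranking literally and on follow-up records each carrying their own outcome. The size is unknown and may be zero. Incidence, seriousness, relatedness and the primary efficacy analysis are unaffected, and any error overstates unresolved events. It is a minor correction to descriptive safety tables, worth making because it is simple.

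**What to change.** Replace the Outcome row of the table in SAP section 4.7.2 with this rule:

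> Fatal if any follow-up is fatal; otherwise the outcome of the last follow-up with a known outcome; Unknown only if no follow-up has a known outcome.

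Leave the end date and ongoing rows, and the recovered-only condition for the duration summary, as they are. A plain last-record rule is not recommended, because it would discard a known status whenever the final record is Unknown.

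The cost is one row of the SAP and the matching line of programming. No new data are needed, and if no event has an affected pattern the outputs do not change.
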